## 1. RCT Details

This section provides a high-level overview of a **published** RCT that the described real-world evidence study is trying to replicate as closely as possible given the remaining limitations inherent in the healthcare databases.

### 1.1 Title

**Cardiovascular Safety of Degarelix Versus Leuprolide for Advanced Prostate Cancer ([PRONOUNCE Trial](#))**

### 1.2 Intended aim(s)

To compare the incidence of major cardiovascular events (MACE) among advanced prostate cancer subjects treated with degarelix versus leuprolide.

### 1.3 Primary endpoint for replication

Time from randomization to the first confirmed, adjudicated occurrence of a MACE, which is defined as a composite of all-cause death, nonfatal myocardial infarction, or nonfatal stroke through 12 months of ADT treatment.

### 1.4 Required power for primary endpoint and noninferiority margin (if applicable)

Based on prior literature, it was determined that 66 MACE events and 876 subjects would be required to reject a two-sided null hypothesis of equal hazards with 80% power at a 5% type I error rate. A hazard ratio of 0.49 with absolute event rates of 5.1% and 10.2% (degarelix vs leuprolide) were hypothesized.

### 1.5 Secondary endpoint for replication (assay sensitivity) and RCT finding

Secondary cardiovascular objectives: To assess 1) the frequency of MACE components individually (i.e., nonfatal myocardial infarction, nonfatal stroke, and all-cause mortality)

### 1.6 Trial estimate

The trial is ongoing and scheduled to complete in April 2021.

### 3. Data Source(s)

Optum CDM, IBM® MarketScan®, Medicare Diabetes

### 4. Study Design Diagram

The study design diagram visualizes key aspects of the longitudinal study design for expedited review.

Figure 1.

## 5. Cohort Identification

### 5.1 Cohort Summary

An active-comparator, incident-user design will be employed to compare patients that received degarelix vs. leuprolide. Subjects will be selected on the basis of having at least one diagnosis code indicating prostate cancer, male sex, and a history of atherosclerotic cardiovascular disease. Subjects will be excluded if they were not treatment-naïve with respect to prostate cancer, had a record of uncontrolled diabetes or hypertension within 30 days prior to treatment initiation, had a history of long QT syndrome or risk factors thereof (i.e., heart failure, hypokalemia, or medications known to prolong the QT interval), or an acute myocardial infarction, stroke, or revascularization procedure within 30 days prior to treatment initiation. In contrast to the PRONOUNCE trial, patients cannot be required to have had established tumor staging information, angiography-verified stenosis/occlusion of vessels, and a lack of planned cardiac surgery at the time of treatment initiation due to poor capture of this information in administrative data. All patients were required to have continuous enrollment for 365 days prior to cohort entry to ensure incident use of the study drugs.

### 5.2 Important steps for cohort formation

Incident use of the exposure (leuprolide or degarelix) is defined as no use of the exposure drug in the 365 days prior to meeting all eligibility criteria and initiation of exposure.

#### 5.2.1 Eligible cohort entry dates

The degarelix indication for treatment of prostate cancer was approved by the FDA on Dec 24, 2008. Leuprolide was initially approved for the same indication prior to Dec 24, 2008.

- IBM® MarketScan®: Dec 24, 2008 – December 31, 2018 (end of available data)
- Optum CDM: Dec 24, 2008 – June 30, 2020 (end of available data)
- CMS Diabetes: Dec 24, 2008 – Dec 31, 2017 (end of available data)

#### 5.2.2 Specify inclusion/exclusion criteria for cohort entry and define the index date

Inclusion and exclusion criteria were adapted from the trial as closely as possible. Definitions for all inclusion/exclusion are provided in **Appendix** and are summarized in the flowcharts below.

### 5.3 Flowchart of the study cohort assembly

For Degarelix vs Leuprolide

	IBM® MarketScan®		Optum CDM		CMS - Diabetes	
	Less Excluded Patients	Remaining Patients	Less Excluded Patients	Remaining Patients	Less Excluded Patients	Remaining Patients
All patients in our database		200,203,908		78,202,636		23,466,175
Patients with Degarelix/Leuprolide [measured between Dec 24, 2008 and Dec 31, 2019.]	-199,937,514	266,394	-78,046,787	155,849	-23,212,628	253,547
Excluded due to insufficient enrollment [-365, 0]	-94,870	171,524	-36,242	119,607	-125,589	127,958
After wash-out for prior use of reference (Leuprolide) [-365, -1]	-106,281	65,243	-77,869	41,738	-96,813	31,145
After wash-out for prior use of exposure (Degarelix) [-365, -1] and Excluded because patient qualified in >1 exposure category	-1,961	63,282	-2,153	39,585	-3,397	27,748
Inclusion only Male gender [-365, 0]	-43,683	19,599	-17,401	22,184	-183	27,565
Inclusion Prostate Cancer [start of all available data, 0]	-784	18,815	-502	21,682	-210	27,355
Inclusion Pre-existing ASCVD [start of all available data, -30]	-14,187	4,628	-15,729	5,953	-16,099	11,256
Exclusion Androgen deprivation therapy (GnRH agonists/antagonists) [-365, 0]	-145	4,483	-106	5,847	-465	10,791
Exclusion Androgen deprivation therapy (hormonal therapy) [-365, -14] and Exclusion Androgen deprivation therapy (Orchiectomy) [start of all available data, 0]	-575	3,908	-748	5,099	-1,768	9,023
Exclusion Uncontrolled Diabetes [-30, 0]	0	3,908	0	5,099	0	9,023
Exclusion Uncontrolled Hypertension [-30, 0]	-28	3,880	-19	5,080	-97	8,926
Exclusion Heart failure [starts of all available data, 0]	-285	3,595	-556	4,524	-1,602	7,324
Exclusion QT syndrome [starts of all available data, 0]	-7	3,588	-9	4,515	-19	7,305

Exclusion Hypokalemia [-90, 0]	-3	3,585	-14	4,501	-37	7,268
Exclusion Hypomagnesemia [-90, 0]	-9	3,576	-7	4,494	-12	7,256
Exclusion QT prolonging medicines [0, 0]	-192	3,384	-191	4,303	-446	6,810
Exclusion Acute MI [-29, 0]	-6	3,378	-9	4,294	-11	6,799
Exclusion Stroke [-29, 0] and Exclusion Revascularization [-29,0]	-9	3,369	-16	4,278	-29	6,770
Final cohort		3,369		4,278		6,770

\*\*Certain exclusion criteria are in collapsed form to maintain compliance with CMS' cell suppression policy\*\*

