1 Histologically confirmed adenocarcinoma of the prostate	Measured from [start of all available data, 0]. Must have both diagnosis code and male gender for inclusion. Malignant Neoplasm of the Prostate ICD-9 diagnosis: 188.0-188.9 ICD-10 diagnosis: C61.0 (inpatient and outpatient) Sex: Male		Male patients with ICD-9 - an exposure provides enough information to confirm diagnosis, as the exposures have very few or no indications outside of advanced PC	
2 Tumor, node, metastasis staging available before treatment start (bone scan and/or CT scan and/or MRI) <12 weeks before study start			Necessitating code for biopsy may exclude subjects with apparent prostate cancer if they were initially diagnosed prior to database enrollment with early stage disease	
3 Investigator judgement to initiate combined ADT therapy with intended duration of 12 months or longer			Lupron is indicated in females for endometriosis. Restricting to males helps ensure indication of interest.	
4 Patients with prostate cancer who developed metastases after local therapy				
5 -Patients with prostate cancer with very high-risk, high-risk, or intermediate risk disease with feature of unfavorable prognosis who will be treated with definitive radiation therapy in combination with at least 12 months of neoadjuvant/adjacent ADT				
		Measured from [start of all available data, 30] on an inpatient or outpatient care setting in any diagnosis position		
		Acute or old MI: ICD-9 diagnosis: 410.xx, 412.xx ICD-10 diagnosis: I21.00-I21.09, I21.10-I21.19, I21.21, I21.29, I21.3, I21.4, I22.0, I22.1, I22.2, I22.8, I22.9, I25.2		

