## Appendix A

**Optum****MarketScan****Medicare**

All variables under Table 1 is used in PS matching except Radiation therapies used in Prostate cancer, Chemo therapies used in Prostate cancer and Lithium

All variables under Table 1 is used in PS matching except HIV/AIDS, Radiation therapies used in Prostate cancer, Chemo therapies used in Prostate cancer and Lithium

All variables under Table 1 is used in PS matching except Lithium

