...3 - South; n (%)	1,352 (36.7%)	221 (37.0%)		-0.01	914 (31.1%)	137 (31.8%)	-0.02	2,336 (40.1%)	375 (39.9%)	0.00	4,602 (37.0%)	733 (37.2%)
...4 - West; n (%)	925 (25.1%)	131 (21.9%)		0.08	420 (14.3%)	49 (11.4%)	0.09	988 (16.9%)	147 (15.6%)	0.04	2,333 (18.7%)	327 (16.6%)
Race												
...White; n (%)	2,727 (74.1%)	448 (75.0%)		-0.02	-----	-----	4,818 (82.7%)	806 (85.7%)	-0.08	7,545 (60.6%)	1,254 (63.7%)	-0.06
...Asian; n (%)	75 (2.0%)	11 (1.8%)		0.01	-----	-----	N/A	N/A	N/A	N/A	N/A	N/A
...Black; n (%)	346 (9.4%)	62 (10.4%)		-0.03	-----	-----	628 (10.8%)	86 (9.1%)	0.06	974 (7.8%)	148 (7.5%)	0.01
...Hispanic; n (%)	228 (6.2%)	39 (6.5%)		-0.01	-----	-----	N/A	N/A	N/A	N/A	N/A	N/A
...North American Native; n (%)	-----	-----		-----	-----	-----	N/A	N/A	N/A	N/A	N/A	N/A
...Other; n (%)	-----	-----		-----	-----	-----	108 (1.9%)	16 (1.7%)	0.02	108 (1.9%)	16 (1.7%)	0.02
Cardiovascular event prognosticators												
Acute or Old MI; n (%)	1,428 (38.8%)	232 (38.9%)		0.00	713 (24.3%)	97 (22.5%)	0.04	2,039 (35.0%)	354 (37.6%)	-0.05	4,180 (33.6%)	683 (34.7%)
Anxiety; n (%)	228 (6.2%)	37 (6.2%)		0.00	125 (4.3%)	24 (5.6%)	-0.06	399 (6.8%)	58 (6.2%)	0.02	752 (6.0%)	119 (6.0%)
Atrial Fibrillation; n (%)	633 (17.2%)	101 (16.9%)		0.01	387 (13.2%)	73 (16.9%)	-0.10	1,148 (19.7%)	207 (22.0%)	-0.06	2,168 (17.4%)	381 (19.3%)
Coronary Atherosclerosis; n (%)	2,781 (75.6%)	475 (79.6%)		-0.10	2,116 (72.0%)	316 (73.3%)	-0.03	4,790 (82.2%)	776 (82.5%)	-0.01	9,687 (77.8%)	1,567 (79.6%)
Coronary, Carotid, Iliac, Femoral, and Popliteal Revascularization (Angioplasty/Stent/CABG); n (%)	358 (9.7%)	50 (8.4%)		0.05	269 (9.2%)	35 (8.1%)	0.04	611 (10.5%)	71 (7.5%)	0.10	1,238 (9.9%)	156 (7.9%)
Diabetes with Complications; n (%)	1,297 (35.2%)	208 (34.8%)		0.01	357 (12.2%)	63 (14.6%)	-0.07	4,642 (79.6%)	736 (78.2%)	0.03	6,296 (50.6%)	1,007 (51.1%)
Diabetes without Complications; n (%)	747 (20.3%)	131 (21.9%)		-0.04	945 (32.2%)	143 (33.2%)	-0.02	2,203 (37.8%)	355 (37.7%)	0.00	3,895 (31.3%)	629 (31.9%)
DVT; n (%)	150 (4.1%)	27 (4.5%)		-0.02	108 (3.7%)	6 (1.4%)	0.15	257 (4.4%)	43 (4.6%)	-0.01	515 (4.1%)	76 (3.9%)
Edema; n (%)	344 (9.3%)	68 (11.4%)		-0.07	178 (6.1%)	30 (7.0%)	-0.04	721 (12.4%)	138 (14.7%)	-0.07	1,243 (10.0%)	236 (12.0%)
Erectile dysfunction; n (%)	455 (12.4%)	82 (13.7%)		-0.04	265 (9.0%)	44 (10.2%)	-0.04	705 (12.1%)	123 (13.1%)	-0.03	1,425 (11.4%)	249 (12.6%)
Foot ulcer; n (%)	90 (2.4%)	23 (3.9%)		-0.09	52 (1.8%)	10 (2.3%)	-0.04	262 (4.5%)	49 (5.2%)	-0.03	404 (3.2%)	82 (4.2%)

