Hyperlipidemia; n (%)	3,088 (83.9%)	511 (85.6%)		-0.05	1,865 (63.5%)	302 (70.1%)	-0.14	5,283 (90.6%)	858 (91.2%)	-0.02	10,236 (82.2%)	1,671 (84.9%)
Hypertension; n (%)	3,188 (86.6%)	522 (87.4%)		-0.02	2,192 (74.6%)	331 (76.8%)	-0.05	5,428 (93.1%)	880 (93.5%)	-0.02	10,808 (86.8%)	1,733 (88.0%)
Intracranial or Retroperitoneal Hemorrhage; n (%)	54 (1.5%)	5 (0.8%)		0.07	20 (0.7%)	5 (1.2%)	-0.05	N/A	N/A	N/A	N/A	N/A
Ischemic Heart Disease; n (%)	3,026 (82.2%)	504 (84.4%)		-0.06	2,250 (76.6%)	333 (77.3%)	-0.02	5,000 (85.8%)	806 (85.7%)	0.00	10,276 (82.6%)	1,643 (83.4%)
Ischemic Stroke; n (%)	644 (17.5%)	119 (19.9%)		-0.06	497 (16.9%)	79 (18.3%)	-0.04	1,510 (25.9%)	232 (24.7%)	0.03	2,651 (21.3%)	430 (21.8%)
Major Trauma; n (%)	196 (5.3%)	30 (5.0%)		0.01	117 (4.0%)	21 (4.9%)	-0.04	410 (7.0%)	56 (6.0%)	0.04	723 (5.8%)	107 (5.4%)
Obesity; n (%)	524 (14.2%)	68 (11.4%)		0.08	252 (8.6%)	47 (10.9%)	-0.08	976 (16.7%)	164 (17.4%)	-0.02	1,752 (14.1%)	279 (14.2%)
Other Disorders of Thyroid Gland; n (%)	112 (3.0%)	18 (3.0%)		0.00	69 (2.3%)	13 (3.0%)	-0.04	262 (4.5%)	38 (4.0%)	0.02	443 (3.6%)	69 (3.5%)
Overweight; n (%)	294 (8.0%)	46 (7.7%)		0.01	83 (2.8%)	13 (3.0%)	-0.01	208 (3.6%)	42 (4.5%)	-0.05	585 (4.7%)	101 (5.1%)
PE; n (%)	59 (1.6%)	10 (1.7%)		-0.01	39 (1.3%)	2 (0.5%)	0.08	99 (1.7%)	14 (1.5%)	0.02	197 (1.6%)	26 (1.3%)
Peripheral Vascular Disease; n (%)	1,234 (33.5%)	205 (34.3%)		-0.02	705 (24.0%)	117 (27.1%)	-0.07	1,798 (30.8%)	277 (29.4%)	0.03	3,737 (30.0%)	599 (30.4%)
Stable Angina; n (%)	490 (13.3%)	83 (13.9%)		-0.02	276 (9.4%)	37 (8.6%)	0.03	769 (13.2%)	115 (12.2%)	0.03	1,535 (12.3%)	235 (11.9%)
Systemic Embolism; n (%)	60 (1.6%)	11 (1.8%)		-0.02	49 (1.7%)	10 (2.3%)	-0.04	N/A	N/A	N/A	N/A	N/A
TIA; n (%)	90 (2.4%)	22 (3.7%)		-0.08	63 (2.1%)	10 (2.3%)	-0.01	266 (4.6%)	36 (3.8%)	0.04	419 (3.4%)	68 (3.5%)
General Health/Mortality Prognosticators												
Abnormal liver function; n (%)	333 (9.0%)	55 (9.2%)		-0.01	189 (6.4%)	28 (6.5%)	0.00	574 (9.8%)	97 (10.3%)	-0.02	1,096 (8.8%)	180 (9.1%)
Alcohol Abuse/Dependence; n (%)	72 (2.0%)	17 (2.8%)		-0.05	33 (1.1%)	5 (1.2%)	-0.01	108 (1.9%)	19 (2.0%)	-0.01	213 (1.7%)	41 (2.1%)
Anemias (Sickle-Cell, G6PD Deficiency, Nutrient Deficiency); n (%)	840 (22.8%)	157 (26.3%)		-0.08	492 (16.7%)	72 (16.7%)	0.00	1,970 (33.8%)	286 (30.4%)	0.07	3,302 (26.5%)	515 (26.2%)
Asthma; n (%)	150 (4.1%)	22 (3.7%)		0.02	106 (3.6%)	22 (5.1%)	-0.07	351 (6.0%)	58 (6.2%)	-0.01	607 (4.9%)	102 (5.2%)

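### The propensity score pools acute and old MI and shows no time-since-event term, so balance on its MI row does not show balance on recent MI

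*Combined protocol and SAP*

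**What the plan says.** **Eligibility.** The flowchart in Section 5.3 has the step "Inclusion Pre-existing ASCVD [start of all available data, -30", so a qualifying code may be years old or 30 days old. The recent-event exclusion is "Exclusion Acute MI [-29, 0", and stroke and revascularization use the same 30-day window. A man is therefore eligible from day 30 after such an event.

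**Codes.** The MI item in Appendix A's cardiovascular inclusion criterion puts acute and old MI under one label: "ICD-9 diagnosis: 410.xx, 412.xx ICD-10 diagnosis: I21.00-I21.09" and so on, ending with the ICD-10 code for old MI.

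**Score.** For Medicare the appendix states "All variables under Table 1 is used in PS matching except Lithium". Optum and MarketScan drop a few more rare rows. The event rows of Table 1 are "Acute or Old MI; n", "Ischemic Stroke; n" and "Coronary, Carotid, Iliac, Femoral, and Popliteal Revascularization (Angioplasty/Stent/CABG); n". None is split by time since the event. Apart from a 365-day label on the frailty score, the readable text gives no look-back window for Table 1 covariates.

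**Follow-up.** In Sections 7 and 9 the as-treated median is 89 days for leuprolide in every database. For degarelix it is 82 days in Optum and 67 or 68 in the other two. The secondary intention-to-treat analysis (Section 6.3.2) does not stop at discontinuation or switching, but keeps the 365-day limit.

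**The concern.** The plan treats the timing of an event as important enough to exclude the last 30 days. Beyond that it shows no timing term. The cohort mixes men a few weeks after an MI, stroke or revascularization with men whose event was long ago. On the MI row these men look alike.

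Over a follow-up of about three months, time since the last event could plausibly predict MACE, and it could influence the choice between the two drugs in men with heart disease. The documents state neither premise. If both hold, and recency differs between arms after matching, the HR is confounded. The Table 1 balance check as built could not reveal this, because the MI row can agree while its recent part does not.

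**Working it through.** **1. The plan's own figures.** The pooled risk is (108 + 43 + 211)/(4,272 + 3,367 + 6,769) = 362/14,408 = 25.12 per 1,000, as stated. Expected events after matching are 3,774 × 25.12/1,000 = 94.80. Schoenfeld power at HR 0.49, two-sided 0.05 and 1:1 allocation is 0.9348, against 0.93484302 in Section 10. The point changes none of these, except through any pairs lost in a re-match.

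**2. What the MI row shows (Table 1, pooled).**
- Unmatched: leuprolide 4,180/12,448 = 33.6%; degarelix 683/1,969 = 34.7%.
- Matched: leuprolide 658/1,887 = 34.9%; degarelix 654/1,887 = 34.7%.

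The row balances. It counts any MI, however old.

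**3. How many recent events there may be.** Recency is not reported, so I scale from the exclusion counts in Section 5.3 (MarketScan, Optum, CMS).
- Men before the MI exclusion: 3,384 + 4,303 + 6,810 = 14,497.
- Removed for MI on days -29 to 0: 6 + 9 + 11 = 26 (0.18%).
- Removed for stroke or revascularization: 9 + 16 + 29 = 54.
- All three: 80 (0.55%).
- Final cohort: 3,369 + 4,278 + 6,770 = 14,417.

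Assume a constant rate. Days -365 to -30 are 336 days.
- MI: 26/30 × 336 = 291 men, 291/14,417 = 2.0%.
- Any of the three: 80/30 × 336 = 896 men, 896/14,417 = 6.2%.

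These are rough. The exclusions are applied in sequence, and a man with two events over the year would be counted twice. In the other direction, the 80 men already had a qualifying code by day -30, whereas a man whose first event falls on days -365 to -30 qualifies through that event.

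A recent MI is thus about 2.0/34.8, or 6%, of the pooled MI row. An imbalance in that part could leave the row total almost unchanged.

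**4. Size of the possible bias.** With prevalence of a recent event p_D (degarelix) and p_L (leuprolide), and hazard ratio r for a recent event against none:

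bias factor = [1 + p_D(r − 1)] / [1 + p_L(r − 1)]

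A 7% v 5% split averages 6%, in line with step 3. The split and r are assumptions.

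| r | degarelix 7%, leuprolide 5% | degarelix 5%, leuprolide 7% |
|---|---|---|
| 2 | 1.07/1.05 = 1.019 | 1.05/1.07 = 0.981 |
| 3 | 1.14/1.10 = 1.036 | 1.10/1.14 = 0.965 |
| 4 | 1.21/1.15 = 1.052 | 1.15/1.21 = 0.950 |

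MI alone matters less. At 2.5% v 2.0% and r = 4 the factor is 1.075/1.060 = 1.014. All these factors treat recency as wholly unadjusted.

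**5. Scale against random error.** With 94.80 events, SE(log HR) = 2/√94.80 = 0.205, and the 95% interval multiplier is exp(1.96 × 0.205) = 1.50. The possible bias is small beside this, although the interval does not allow for confounding.

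**The case against.** **The score is not blind to recency.** It also holds any hospitalization, four categories of cardiology visits, stable angina, ischemic heart disease, antiplatelets, beta blockers, nitrates, statins and frailty. A man weeks after an MI would usually differ on several of these. A reader might infer that he is matched as if equal to a man with an old MI. That is true of the MI row only, not of the score. This part of the objection stands.

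**The windows are not known.** The stroke and revascularization rows may already be limited to, say, a year. The readable text does not settle it, and the design diagram is not reproduced there. This also stands, and the fix is conditional on it.

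**Channelling is not shown.** A reader might infer that degarelix men had more recent events, so that a benefit is partly hidden. Two Optum figures invite this: 3-5 cardiology visits before matching (18.1% leuprolide v 24.5% degarelix, standardized difference -0.16) and revascularization after matching (5.5% v 7.9%, -0.10). The pooled differences are only -0.05 and -0.03. Matched MarketScan revascularization runs the other way (40 v 32 men). Pooled unmatched hospitalization (27.2% v 25.4%) and nitrates (20.1% v 18.4%) are higher for leuprolide. The cardiology variable is itself in the score. The documents support no direction.

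**A larger bias is not supported.** A 15% v 10% split at r = 4 gives 1.45/1.30 = 1.115, but its average of 12.5% is about twice the 6.2% from the exclusion counts.

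**Not every analysis is that short.** The 89 days is the overall and leuprolide median, and the intention-to-treat analysis runs longer. The eligibility window is adapted from the trial and is not itself a defect.

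The objection leaves untouched that acute and old MI share one row, and that balance on it cannot show balance on recent MI.

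**Conclusion.** The point holds as a refinement of the covariates. Men are eligible from day 30 after an event, the score pools acute with old MI, and no time-since-event term is shown for MI, stroke or revascularization. Agreement at 34.9% v 34.7% is therefore no evidence on recent MI.

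The likely size is modest: about 2% to 5% on the HR, in either direction, before allowing for the proxies. That rests on three assumptions: a constant event rate carried back from the 30-day exclusions, a 7% v 5% split between arms, and two to four times the hazard after a recent event. Recency by arm is not reported, so an imbalance is neither shown nor ruled out.

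**What to change.** State the look-back window of each Table 1 covariate. Then, in each database:

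1. Replace the single MI row by (a) an acute MI code on days -365 to -30 and (b) an older or history-only MI code.
2. Add indicators for stroke and for revascularization on days -365 to -30, unless those rows already use that window.
3. Re-run the 1:1 match at the Section 9 stage, still with the dummy outcome, and report the new rows by arm in Table 1 before and after matching.
4. Update the Section 10 power if the number of pairs changes.

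The MI and revascularization codes are in Appendix A, and the plan already needs a stroke definition for its exclusion and outcome. The Section 10 review dates are blank and Section 13 holds no results, so in the document as it stands this can be done before outcomes are compared. The cost is three or four binary covariates, one re-match and possibly a few lost pairs. Small cells may need collapsing in the CMS data under the suppression policy noted in Section 5.3.

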## 6. Variables

### 6.1 Exposure-related variables:

#### Study drug:

The study exposure of interest is defined by a HCPCS/CPT code or outpatient prescription drug claim indicating degarelix administration or dispensation, respectively. New initiation will be defined by no such records of degarelix in the prior 365 days before treatment initiation (washout period) and fulfillment of study eligibility criteria.

#### Comparator agent:

The comparator is defined by an HCPCS/CPT code or outpatient prescription drug claim indicating leuprolide administration or dispensation, respectively. New initiation will be defined by no such records of leuprolide in the prior 365 days before treatment initiation (washout period) and fulfillment of study eligibility criteria.

### 6.2 Preliminary Covariates:

- Age

The covariate listed above represents only a small subset of the covariate vector that will ultimately be controlled for in the design and analysis. We use the covariate above only for initial feasibility analyses to judge whether there is likely to be sufficient overlap between treatment groups to proceed with the study. Remaining covariates are defined only after the study has passed the initial feasibility analysis and the initial power assessment and are listed in Table 1 (**Appendix B**). Gender is not included since the study is already restricted to male subjects.

### 6.3 Outcome variables and study follow-up:

#### 6.3.1 Outcome variables

Effectiveness outcome variables of interest (definitions provided in **Appendix**):

- **Primary outcome:** MACE (all-cause death, nonfatal myocardial infarction, or nonfatal stroke through 12 months of primary treatment with leuprolide or degarelix)
- Secondary outcomes:
  - Secondary cardiovascular objectives: To assess 1) the frequency of MACE components individually (i.e., nonfatal myocardial infarction, nonfatal stroke, and all-cause mortality)

#### 6.3.2 Study follow-up

Both as-treated (AT) and intention-to-treat (ITT) analyses will be conducted with treatment defined as the index drug on day of cohort entry. An allowable gap of 90 days between records indicating each treatment will qualify as “continuous therapy” with respect to follow-up in the as-treated analysis.

The follow-up will start the day after drug initiation (i.e., cohort entry date), and will continue until the earliest date of the following events:

- The first occurrence of the outcome of interest,
- The date of end of continuous registration in the database,
- End of the study period,
- Measured death event occurs,
- 365 days
- Switch
- Discontinuation (90 days allowable grace period and risk window)

In the secondary ITT analysis, we will not censor for discontinuation or switching among study drugs

